12. PRIMARY CARE QUALITY INDICATOR OUTCOME

DEFINITIONS AND ANALYSES

Objective

Trial objective: To compare health care quality provided to children with asthma by CYPHP intervention practices compared with EUC practices.

Primary care quality indicators for asthma, eczema and constipation were taken from national guidelines³⁻⁵ and published literature,⁶ and were selected by clinician consensus on relevance to CYP and whether the indicator was measurable using coded primary care data and/or audit of primary care data, including notes.

12.1 Asthma Quality Indicator Definitions

For determining annual action plan creation or amendment, annual asthma review, asthma control test and documented height, each child will be observed for 450 days from the later date of 1) when asthma was first identified or 2) the start of the study (April 2018). The follow-up time was extended to more than 12 months, to allow for any disruption that may occur during COVID lockdown.

Prescribing a spacer is not an annual event and we will investigate spacer prescribing any time after the asthma was first identified.

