8. STUDY POPULATIONS

8.1 Health Service Use Population level populations

Inclusion criteria:

- Aged 0-15 (<16) years
 - Within the study period (April 2018 to June 2020)
- Registered with a randomised Southwark or Lambeth GP practice
 - Within the study period (April 2018 to June 2020)

This will be an open cohort, including children who register with a GP practice during the course of the trial. Trial arm assignment is described in section 18.

Exclusion criteria:

We excluded children who had <30 days observation time. Reasons for short observation time include

- Children turning 16 years shortly after the start of the trial period,
- Children registering with a GP practice shortly before the end of the trial period.

➤ Randomised population

Intervention and control only, *excluding* pilot clusters or practices where the randomisation allocation could not be determined.

➤ Quasi-experimental population

Intervention, control *and* pilot clusters

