8.2 Health Service Use Tracer condition populations

Subset of populations in section 8.1, excluding those without a tracer condition (asthma, constipation, or eczema).

Definition of tracer condition: Uses the same methodology applied by the CYPHP call/recall system, i.e. diagnosis, disease management, or therapy codes in the primary care record, and age restrictions. The clinical (Read/SNOMED) codes and therapies are listed in Appendix. For all conditions, an individual's complete records are interrogated.

If a subject meets the call/recall criteria for a tracer condition, they are defined as having a tracer condition from the first recorded event used in the definition (e.g. if they are defined as having asthma due to having an asthma diagnosis or three prescriptions of asthma medication in one year, we define their asthma 'start date' as the date of the first of those prescriptions or diagnosis).

We treat all conditions as ongoing, i.e. the observation period is continuous from the 'start date' of their condition (described above) until their observation 'end date' which occurs when they leave a GP practice, turn 16 years of age, or reach the end of the study period.

➤ Randomised HSU Tracer condition population

Intervention and control only, *excluding* pilot clusters

Subpopulations:

- Asthma
- Eczema
- Constipation

➤ Quasi-experimental HSU Tracer condition population

Intervention, control *and* pilot clusters

Subpopulations:

- Asthma
- Eczema
- Constipation

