9.4 Primary care quality measures

Asthma

1. Proportion of CYP aged 5 years and over with asthma have a recorded personalised action plan.
2. Proportion of CYP aged 5 years and over with asthma have asthma review over a 12-month period.

3. Proportion of CYP aged 5 years and over with asthma have asthma control monitored at their asthma review.
4. Proportion of CYP aged 5 years and over with asthma have documented height at their asthma review.
5. Proportion of CYP who receive treatment in an emergency care setting for an asthma attack are followed up by their GP within 30 working days of discharge.
6. Proportion of CYP with asthma prescribed a spacer
7. Proportion of CYP with asthma have psychosocial assessment in addition to physical severity

Constipation

1. Proportion of CYP with diagnosed constipation receive oral macrogols as first-line treatment.
2. Proportion of CYP starting maintenance therapy have their first treatment review by a healthcare professional within 6 weeks.
3. Proportion of CYP with asthma have psychosocial assessment in addition to physical severity

Eczema

1. Proportion of CYP with atopic eczema are offered treatment based on recorded eczema severity.
2. Proportion of CYP with atopic eczema are prescribed sufficient quantities (250–500 g weekly) from a choice of unperfumed emollients for daily use.
3. Proportion of CYP of children with atopic eczema who have a repeat prescription of moderate/very potent topical steroids
4. Proportion of CYP with atopic eczema have psychosocial assessment at every eczema consultation.

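### The 450-day window for the asthma quality indicators can begin before the child joined the randomised practice, because registration date is missing from the start rule, and the date for judging age 5 is not fixed

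*SAP*

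**What the plan says.** Section 12.1 sets the window for the action plan, annual review, control test and height indicators: "each child will be observed for 450 days from the later date of 1) when asthma was first identified or 2) the start", the second date being given as April 2018. It explains the length, but not the starting point: "The follow-up time was extended to more than 12 months, to allow for any disruption that may occur during COVID lockdown".

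Three other parts of the SAP bear on that rule.

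- **Section 8.1**, on the population: "This will be an open cohort, including children who register with a GP practice during the course of the trial".
- **Section 8.2**, on dating a tracer condition. Children meeting the criteria count from the earliest qualifying record: "they are defined as having a tracer condition from the first recorded event used in the definition". The look-back is unlimited: "For all conditions, an individual's complete records are interrogated". The definition draws on "diagnosis, disease management, or therapy codes in the primary care record, and age restrictions"; the age values are in an appendix file that is not shown.
- **Section 9.4**, on the four indicators concerned, which are limited by age, for example "Proportion of CYP aged 5 years and over with asthma have a recorded personalised action plan" and "Proportion of CYP aged 5 years and over with asthma have asthma review over a 12-month period". No reference date for age is given.

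Section 12 states its objective as comparing the quality of care given by intervention practices with that given by enhanced usual care practices. Section 12.2 analyses the indicators by random-effects logistic regression at child level, with clustering by GP hub.

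**The concern.** A process-of-care indicator is meaningful only for time during which the practice being judged was responsible for the child. Section 12.1 takes the later of two dates, and neither is the date on which that responsibility began. In an open cohort with whole-record dating of asthma, the clock can run, and even stop, before the child reaches the practice.

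Care given earlier may appear in the extract as another practice's work, or may be absent and scored as not done. The SAP does not settle which. In neither case does the result describe the assigned practice. A child-level logistic model without a time-at-risk term has nothing to correct this, unlike the rate outcomes in section 10.1, which use observed person-time.

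Age raises a smaller question. If the date for judging age 5 is not fixed, two analysts could form different denominators, and one of these could include time below the indicator's own age limit.

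**Working it through.** The SAP gives no figure for the number of children affected, so there is none to reproduce. The check is date arithmetic on the SAP's own dates, followed by an illustration on stated assumptions. Section 12 does not name its analysis population. I take asthma to be dated as in section 8.2, which holds the SAP's only dating rule.

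**Inputs from the SAP.** Trial start 1 April 2018 (7.1). Window W = 450 days = 450/365.25 = 1.23 years (12.1). Study end 30 June 2021 (7.1) or June 2020 (8.1), taken as 30 June 2020. The two ends conflict, so both are carried through: 821 days (Y = 2.25 years) and 1,186 days (Y = 3.25 years) after the start.

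**Step 1: the window for established asthma.** If asthma was identified before April 2018, the later of the two dates is always the trial start. 1 April 2018 + 450 days = 25 June 2019.

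- Registered after 25 June 2019: the whole window precedes joining.
- Registered during the trial but before that date: part of the window precedes joining.

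This step needs no assumption beyond the dating rule.

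**Step 2: how many children (assumption).** Let r be the yearly number of joiners with asthma identified before April 2018, as a fraction of the asthma list at the start, arriving evenly. The SAP does not give r; I use 2% to 15%.

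- Wholly pre-registration: r(Y − W)/(1 + rY)
- Partly pre-registration: rW/(1 + rY)

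| r per year | End June 2020: wholly / partly | End June 2021: wholly / partly |
|---|---|---|
| 2% | 1.9% / 2.4% | 3.8% / 2.3% |
| 5% | 4.6% / 5.5% | 8.7% / 5.3% |
| 10% | 8.3% / 10.1% | 15.2% / 9.3% |
| 15% | 11.4% / 13.8% | 20.3% / 12.4% |

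For example, r = 15% and the 2021 end give 0.15 × (3.25 − 1.23)/(1 + 0.15 × 3.25) = 20.3% on unrounded inputs. The denominator omits children first diagnosed while registered, who would lower these shares.

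**Step 3: age.** With the window fixed at 1 April 2018 to 25 June 2019, a child under 5 − 1.23 = 3.77 years at the start is under 5 throughout, and one aged 3.77 to 5 is under 5 for part of it.

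- If age is judged at window start, neither child is in the denominator, so the share with under-5 time is 0%.
- If reaching 5 at any time in the study suffices, and ages are uniform with asthma already identified (assumptions), the wholly under-5 share is (Y − W)/(11 + Y): 7.7% for the 2020 end and 14.1% for the 2021 end. The partly under-5 share is W/(11 + Y): 9.3% and 8.6%.

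**Step 4: what a corrected start requires.** A full 450 days needs a start no later than 6 April 2020 for a 30 June 2021 end, or 7 April 2019 for a 30 June 2020 end.

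**The case against.** The best defence is that observation elsewhere in the SAP implies registration. Section 8.1 excludes children with under 30 days of observation and gives late registration as one cause, so observation there cannot begin before joining. Section 10.1 equates time at risk with time under observation, and section 8.2 makes the tracer populations subsets of 8.1. On that view section 12.1 inherits the limit. I do not think this succeeds. Section 8.2 itself starts tracer observation at the condition's start date and ends it on leaving a practice, with no matching start at joining. Section 12.1 then gives an explicit two-term rule. An analyst who programs it as written will include pre-registration time.

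Other parts of the defence stand, and they limit the point. A reader might infer any of the following, and the SAP supports none of them.

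- **That many children are affected.** The SAP has no joiner counts. The shares above rest on assumed rates and on a study end that the SAP states in two ways.
- **That children are scored at an age the indicator excludes.** This happens only if age is judged after window start, which no section says. The tracer definition also has age restrictions that cannot be seen.
- **That a true difference shrinks in proportion to the affected share.** Seventy practices form 23 clusters in two arms (section 1.1). A child who moves within an arm keeps that arm's exposure, and a partial window keeps some effect.

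The indicators are also not among the outcomes labelled primary in section 9.

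**Conclusion.** The point holds in a limited form. As written, section 12.1 leaves registration out of the window start. For a child with asthma identified before April 2018 who joins during the trial, some or all of the window falls before joining. This conflicts with the objective of section 12 and would tend to dilute the comparison between arms.

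The dates are certain given the dating rule in section 8.2; the size is not. About 2% to 20% with a wholly pre-registration window is an illustration for joining rates of 2% to 15% a year and the two possible study ends. A further 2% to 14% would have a partly pre-registration window. The degree of dilution cannot be calculated from the SAP.

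The age issue is an unstated reference date, with an effect from nil upwards depending on how it is settled. The whole matter is worth correcting before analysis, but does not touch the primary outcomes.

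**What to change.** - **Window start.** Use the latest of asthma identification, 1 April 2018, registration with the randomised practice and, for indicators 1 to 4, the fifth birthday. The last term also fixes when age is judged.
- **Events.** Count only those recorded while the child is registered with that practice.
- **Incomplete windows.** Restrict to children with a full 450 days before leaving, turning 16 or study end, or state another rule. Do not score a cut-short window as not done.
- **Study end.** First reconcile sections 7.1 and 8.1, because the end date decides which windows are complete: latest start 6 April 2020 for a 30 June 2021 end, 7 April 2019 for a 30 June 2020 end.
- **Movers.** State the arm for a child who changes practice. Section 17 covers health service use and consented data but does not name these indicators.

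The cost is SAP wording and fewer evaluable children; how many fewer cannot be told from the SAP. Registration and age data are already needed for the population and time-at-risk definitions in sections 8.1 and 10.1. Requiring a full window also selects children who stay registered, so the numbers excluded should be reported by arm and reason.

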7. STUDY TIME PERIODS

7.1 Study timeline and trial periods

CYPHP Funded: October 2016

Staff Recruitment: 1 October 2016 – 31 March 2017

Trial and Service Set up, intervention embedding: 1 April 2017 – 31 March 2018

Trial start: 1 April 2018

Trial period ends: 30 June 2021

See diagram in Appendix.

Baseline health service use data: Use annual rate(s) for financial year(s) (April-March) for 2014/15, 2015/16, 2016/17 (omitting 2017/18 as during set-up period service implementation began in some areas). Using annual rates avoids issues of seasonality. Where only one year of baseline data is needed, use 1 Apr 2016-31 Mar 2017.

Secondary analysis: Using the trial time period 1 July 2020 - 30 June 2021 (the period with most complete embedding of services).

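### The spacer indicator in SAP 12.1 has no trial-start bound and no allowance for earlier spacers, so pre-trial prescribing is scored as a trial outcome

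*SAP*

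**What the plan says.** SAP section 9.4 lists the indicator as "Proportion of CYP with asthma prescribed a spacer". Section 12 states the purpose of the asthma indicators, which is to compare the quality of care given by intervention and enhanced usual care (EUC) practices.

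Section 12.1 sets two windows. For the action plan, review, control test and height, each child is followed for 450 days "from the later date of 1) when asthma was first identified or 2) the start of the study (April 2018"). For the spacer it gives the reason "Prescribing a spacer is not an annual event" and then the rule "we will investigate spacer prescribing any time after the asthma was first identified". The April 2018 bound is absent from the spacer rule, and so is an end date.

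Section 8.2 shows how far back identification can reach: "For all conditions, an individual's complete records are interrogated", and "we define their asthma 'start date' as the date of the first of those prescriptions or diagnosis". Section 7.1 gives "Trial start: 1 April 2018". It also notes that services had begun in some areas during the 2017/18 set-up year.

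Section 12.2 specifies a random-effects logistic model at child level, clustered by GP hub. It names no covariate or exclusion for an earlier spacer.

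**The concern.** An outcome used to compare randomised arms should be able to respond to what the arms did differently. For a child whose asthma was coded years before the trial, a spacer issued soon after that coding settles the outcome before the CYPHP model existed in any practice. Such a child scores as a success in either arm.

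The stated reason, that a spacer prescription does not recur yearly, supports a window longer than 12 months. It does not bear on when the window should open.

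At stake is how a null result would be read. A small difference on this indicator could mean that CYPHP did not change spacer prescribing, or that most children already had a spacer and little room was left for a difference. The indicator as defined cannot tell these apart. Elsewhere the SAP allows for the baseline: section 10.9 lists the baseline rate of the service-use endpoint and section 11.9 the baseline questionnaire score. Section 12.2 has no counterpart.

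**Working it through.** The SAP gives no prevalence, effect size or power for this indicator, so there is no planned figure to reproduce. The check is algebra plus an illustration.

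**Inputs**
- Window, model and objective: SAP 12, 12.1 and 12.2.
- q, the share of children with a spacer before April 2018: not given; assumed range 0 to 0.8.
- p0 and p1, new prescribing after trial start among children without a spacer (EUC, CYPHP): not given; assumed 0.30 and 0.40, with 0.20 and 0.30, and 0.40 and 0.50, as alternatives.
- Two-sided 5% test of two proportions, clustering ignored. With q = 0, 477 children per arm give 90% power for 0.30 against 0.40.

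**Balanced prior prescribing**

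Ever-prescribed proportion in an arm = q + (1 − q)p.

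Difference between arms = (1 − q)(p1 − p0).

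Example with q = 0.6: EUC 0.6 + 0.4 × 0.30 = 0.72; CYPHP 0.6 + 0.4 × 0.40 = 0.76; difference 0.04; odds ratio (0.76/0.24)/(0.72/0.28) = 1.23.

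| q | EUC | CYPHP | Difference | Odds ratio | Power as written, 477 per arm | Power using only the 477 × (1 − q) per arm without an earlier spacer |
|---|---|---|---|---|---|---|
| 0 | 0.30 | 0.40 | 0.10 | 1.56 | 90% | 90% |
| 0.2 | 0.44 | 0.52 | 0.08 | 1.38 | 70% | 83% |
| 0.4 | 0.58 | 0.64 | 0.06 | 1.29 | 48% | 71% |
| 0.6 | 0.72 | 0.76 | 0.04 | 1.23 | 29% | 54% |
| 0.8 | 0.86 | 0.88 | 0.02 | 1.19 | 15% | 30% |

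The last column keeps the difference at 0.10. Restricting the denominator loses children but still gives more power than counting everyone.

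The direction does not depend on the assumed rates. Between q = 0 and q = 0.8 the odds ratio falls from 1.71 to 1.17 for 0.20 against 0.30, and from 1.50 to 1.23 for 0.40 against 0.50.

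**Unbalanced prior prescribing**

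Let the prior shares be q0 in EUC and q0 + d in CYPHP. The ever-prescribed proportion can be written 1 − (1 − q)(1 − p), so

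difference = (1 − q0)(p1 − p0) + d(1 − p1).

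With p1 = 0.40, the second term is 0.6d. At q0 = 0.6 the diluted effect is 0.04, and d = −0.04/0.6 = −0.067 cancels it. A prior share about 7 points lower in the CYPHP clusters would hide the assumed effect entirely; the same imbalance in the other direction would double it to 0.08.

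**The case against.** The strongest defence is that the definition is deliberate and coherent. Ever prescribed since identification measures coverage, it fits the wording in section 9.4, and a child given a spacer earlier is not receiving poor care. This stands for the measure as a description. It does not make it a good outcome for a comparison of arms, because part of it was fixed before the trial.

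Other points stand as limits:
- A reader might infer that no prescription before April 2018 could be affected by allocation. The SAP does not support that. Section 7.1 says some services began in 2017/18, and no randomisation date is given, so prescriptions from that year may be partly exposed. Those from earlier years are not.
- A reader might infer that the definition necessarily biases the result towards no effect. Dilution by (1 − q) requires balanced prior prescribing. Randomisation gives that in expectation, but it was stratified by borough and restricted on deprivation, child population and outpatient referrals, not on prescribing. The hub random effect represents variation between clusters; it does not remove an imbalance that has occurred.
- Section 8.2 defines the service-use tracer populations, and 12.1 does not cite it. Applying its look-back here is an inference. However, the later-of rule in 12.1 itself presupposes that asthma can be identified before April 2018.
- Children first identified after April 2018 have no pre-trial window and are unaffected.
- The spacer is one of seven asthma indicators. None is labelled primary and none carries a power statement.

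**Conclusion.** The point holds in a limited form. As written, 12.1 scores pre-trial spacer prescribing as a trial outcome for children with asthma identified before April 2018, and 12.2 does nothing to offset it. Under balance, the risk difference shrinks by exactly (1 − q), whatever the prescribing rates, and power falls below that of an analysis restricted to children without an earlier spacer in every illustrated case with q above zero. Without balance, the unadjusted contrast can move either way.

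The actual size cannot be computed from the SAP: q and the prescribing rates are assumptions, and clustering is ignored in the power figures. The trial's primary outcomes (non-elective admissions, PedsQL and WEMWBS) are not touched. The change should be made because it is cheap and because a null spacer result would otherwise be uninterpretable, not because the trial's main conclusions depend on it.

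**What to change.** In section 12.1, define the spacer outcome as a first spacer prescription dated on or after the later of asthma identification and 1 April 2018, up to the end of the child's observation in the trial period. Make the denominator children with no spacer on record before that start date. Write the end date out, because section 7.1 ends the trial period on 30 June 2021 while section 8.1 puts the study period at April 2018 to June 2020.

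Keep the ever-prescribed proportion as a descriptive measure, and report it by arm at 1 April 2018 as a baseline characteristic. That also supplies q and shows any imbalance.

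Adding only the April 2018 bound while keeping all children is not enough. It would score children who already have a spacer as failures, and a main-effect adjustment for an earlier spacer would not cure that, since need and the likely effect differ between the two groups.

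The cost is a date filter, a revised denominator and a few sentences of text. The downside is fewer children in the analysis and a different estimand: new spacer prescribing rather than coverage.

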12.2 Asthma Quality Indicator Statistical Analysis

We will use multi-level (random effects) logistic regression (at an individual child level), clustering by GP hub (cluster).

13. PARTICIPANT AND CLUSTER CHARACTERISTIC VARIABLE

DEFINITIONS

13.1 Observed, Measured, or Reported Variables – Participant level

- Gender (all populations)
- Age (all populations)
- Ethnicity (all populations)

Ethnicity codes were categorised in 5 ethnic groups.
Read code match table was developed from published code lists.⁷

- Health Check Social Question responses (tracer condition populations only)

